TITLE: Dual-task Augmented Reality Treatment (DART) for individuals with Parkinson's disease and deep brain stimulation

Study #: NCT06418152

Document Date: November 4, 2024

PI: [name]

DATE MODIFIED: 11/4/2024, Version 2

Project Goal: The goal of this project is to evaluate the safety and preliminary effectiveness of utilizing a digital therapeutic, Dual-task Augmented Reality Treatment (DART) protocol, for the treatment of postural instability and gait dysfunction (PIGD) in individuals with PD with a previously implanted deep brain stimulator (DBS).

Rationale: Postural instability is a cardinal motor symptom of Parkinson's disease (PD), and is often accompanied with non-motor symptoms such as cognitive impairment.¹ Activities of daily living (ADL) frequently involve the simultaneous performance of two or more tasks, such as crossing the street while holding a conversation. The cognitive demands of dual-tasking to perform routine daily activities may lead to increased fall rates relative to healthy peers.²

Multi-Modal Training in PD patients: In order to treat dual-task impairment (difficulty performing two tasks at once), multi-modal treatment (MMT)³ was designed to target PD-specific declines in the areas of cognitive function and gait and posture impairments. Briefly, MMT training consists of simultaneously training a motor and cognitive task. The motor aspect of MMT stresses high velocity, high amplitude training principles while the cognitive aspect stresses commonly impaired cognitive domains in PD such as attention and executive function. An example of an MMT task is marching while spelling words backwards.

Delivery of a Digital Therapeutic via Augmented Reality for the Treatment of PIGD: The MMT intervention is well-suited for integration into an augmented reality (AR) platform as it consists of the patient performing a series of cognitive and motor tasks simultaneously while the patient receives knowledge of performance and results from a therapist. The Microsoft HoloLens is an untethered, AR headset used in applications as broad as teaching anatomy, displaying fine art and gaming. With AR, the user maintains contact with the physical world and the people in it. The HoloLens uses AR technology to place holograms, objects made entirely of projected light, into the user's physical environment; hence creating a first-person mixed reality environment. These holograms can be viewed from different angles and distances, can be two-dimensional or three-dimensional, can appear life-like, can move, be shaped, and change according to interaction with users' or the physical environment in which they are projected, depending on the programming. We previously developed the Dual-task Augmented Reality Treatment (DART), which delivers MMT training on a head-mounted AR display. The DART platform was successfully piloted in 50 individuals with PD who did not have DBS (IRB # 20-207). The results of the project indicate that DART is an effective method of training for individuals with PD. We plan to expand the impact of that project through the investigation of DART in individuals with PD who have previously undergone DBS surgery.

APPROACH: We will conduct a preliminary study with up to 5 participants to determine the safety and preliminary efficacy of the DART platform on individuals with PD and DBS. It is hypothesized that the DART platform will result in few adverse events and will be well-tolerated by individuals with PD and DBS.

Inclusion criteria:

- 1) Adult with a diagnosis of idiopathic PD
- 2) History of deep brain stimulator placement for treatment of PD

Exclusion criteria:

- 1) Medical diagnosis of dementia or any neurocognitive impairment that compromises the ability to provide informed consent.
- 2) >2 errors on the Short Portable Mental Status Questionnaire⁴
- 3) Musculoskeletal or cardiopulmonary issue that limits one's ability to engage in exercise
- 4) Neurological disease other than Parkinson's disease that impacts motor or cognitive function

DART Platform and Intervention: Up to five individuals with PD and DBS will receive the DART intervention. The 16 DART sessions will be delivered over an 8-week period (but not more than 10-weeks). Each DART session will consist of approximately 30-minutes of dual-task activity and will be scheduled over a 1 hour period. A physical therapist or physical therapist assistant will oversee each session.

Exercises will be progressed based on results from the DART platform, feedback from the participant, and the clinical expertise of the physical therapist or physical therapist assistant.

Data Collection: Assessments of motor and non-motor function will be completed for all participants at the following time points: enrollment, midpoint, and end of treatment. Motor and non-motor outcomes are provided in Table 1. Assessments will be conducted in the “on-medication” state (PD medication ~1 hour prior to testing) and with the DBS set to their clinical settings. Research personnel will inquire with the patient during a scheduling telephone call, the timing of their PD medications. All appointments will be scheduled approximately 1 hour after dosage so as to not disrupt the participants standard medication schedule. The outcomes assessor ([name], DPT) will not have access to training performance data; the physical therapist ([name], DPT) performing the training will not be privy to the outcome assessments. Medication reconciliation will be completed at each assessment and levodopa equivalent daily doses (LEDDs) will be determined. Demographic and outcomes variables will be recorded in RedCap. Training and some motor outcome variables will be collected on the HoloLens2. Only a subject ID will be associated with the HoloLens 2 and no PHI is stored on the device. Optional photo/videos will be recorded on willing participants with [name] utilizing his CCF phone. Immediately after the appointment, any photo/videos will be uploaded and stored on a Cleveland Clinic computer behind CCF firewalls.

[figure not shown]

Figure 1: Study flow diagram.

Table 1: Outcome Metrics

Assessment	Description	Primary Outcome
Adverse events	Such as falls, dizziness, and others as a result of the intervention	Number of serious and non-serious adverse events related to the intervention
Two Minute Walk Test	Distance traveled during a 2-minute period under single- and dual-task conditions	Distance (meters)
MDS-UPDRS III	Clinical assessment of PD motor symptoms	Total score
Timed Up and Go Test (TUG)	Stand from chair, walk 3 meters, turn, return to chair under single- and dual-task conditions	Duration (seconds)
Postural sway	Amount of sway in multiple directions	Sway distance (cm)
Cognitive performance	During single- and dual-task conditions	Number of correct responses
System Usability Scale and other usability/satisfaction surveys	Usability of HoloLens and DART protocol technology	Total score
Activities-specific balance confidence scale (ABC)	Balance confidence during daily tasks	Total score
Fall Diary	To track fall events	Number of falls

Power and Statistical Analysis: The sample size (N=5) is reflective of the preliminary nature of the study. A repeated measured ANOVA will be used to compare the group at the three different time points (baseline, midpoint, and end of treatment).

References:

1. Jankovic J. Parkinson's disease: clinical features and diagnosis. *J Neurol Neurosurg Psychiatry*. Apr 2008;79(4):368-76. doi:10.1136/jnnp.2007.131045
4. Pfeiffer E. Short Portable Mental Status Questionnaire for Assessment of Organic Brain Deficit in Elderly Patients. *Journal of the American Geriatrics Society*. 1975;23(10):433-441. doi:DOI 10.1111/j.1532-5415.1975.tb00927.x

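### Does naming PIGD in the goal without requiring it at entry undermine the efficacy results?

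*Combined protocol and SAP*

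**What the plan says.** The Project Goal is to evaluate DART "for the treatment of postural instability and gait dysfunction (PIGD) in individuals with PD with a previously implanted deep brain stimulator (DBS". A later background heading also links the digital therapeutic to PIGD.

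The Approach section describes the study as one "to determine the safety and preliminary efficacy of the DART platform on individuals with PD and DBS", and its hypothesis is that adverse events will be few and tolerability good.

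There are two inclusion criteria: "Adult with a diagnosis of idiopathic PD" and "History of deep brain stimulator placement for treatment of PD". The four exclusions are "Medical diagnosis of dementia or any neurocognitive impairment that compromises the ability to provide informed consent", too many errors on a mental status questionnaire, a musculoskeletal or cardiopulmonary limit on exercise, and another neurological disease. None sets a threshold on gait, balance, falls or dual-task performance.

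Under Data Collection, "Assessments of motor and non-motor function will be completed for all participants at the following time points: enrollment, midpoint, and end of treatment". Table 1 lists the MDS-UPDRS III ("Clinical assessment of PD motor symptoms") as a total score. It also lists the Two Minute Walk Test and TUG, each under single- and dual-task conditions, as well as postural sway, the ABC scale and a fall diary.

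Under Power and Statistical Analysis, "A repeated measured ANOVA will be used to compare the group at the three different time points". The sample size of 5 is justified only by the preliminary nature of the study.

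**The concern.** If the treated condition is PIGD, one expects entry criteria that select for it, or an analysis that separates those who have it from those who do not. The plan has neither. Someone whose gait and balance are well controlled on medication and stimulation could enroll and have little room to improve on the gait and balance outcomes. With five participants, one or two such people could pull the mean change down noticeably. A flat result might then be taken as failure of the therapy in PIGD, and a gain might be credited to PIGD when it arose in people without it. The MDS-UPDRS III total does not settle the matter, since it mixes gait and posture with other motor signs.

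**Working it through.** **1. Which population is the efficacy claim about?**

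| Place | Population or condition named |
|---|---|
| Title | PD and DBS |
| Project Goal | PIGD, in people with PD and DBS |
| Approach: aim and hypothesis | PD and DBS |
| Inclusion criteria | idiopathic PD, past DBS placement |
| DART Platform and Intervention | PD and DBS |

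The Project Goal is the only one of these places that mentions PIGD, and it does so alongside the PD-with-DBS population. The sentence reads naturally as a symptom domain (PIGD) treated in a population (PD with DBS). The Rationale supports this by calling postural instability a cardinal motor symptom of PD, and the earlier pilot of 50 people is described as PD without DBS, with no PIGD requirement. The Approach, which says what the study will determine, matches the criteria.

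**2. Would the data show who had a deficit at entry?** The Two Minute Walk Test, TUG, sway and ABC are Table 1 outcomes, and Data Collection schedules assessments for all participants at enrollment. The plan has no formal PIGD definition and no stated individual-level display. It does have the baseline gait and balance measurements. The MDS-UPDRS III contributes a total only; whether item scores are kept is not documented.

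**3. Could another analysis do better?** A split of five people by PIGD status gives groups such as 4 and 1 or 3 and 2, too small to compare. Relating change to baseline is no remedy, because baseline is part of the change score and regression to the mean would mislead. Restricting entry would select for the deficit, but at the price of sample size and breadth of safety data.

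**4. How large could the effect of mixed entry be?** The plan states no power, effect size or SD, so there is no figure to reproduce. The following is illustration on assumed inputs.

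Let p be the share of eligible people with PIGD (not given; assumed 50% to 90%). The chance that at least one of five lacks it is 1 − p⁵:

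- p = 0.9: 1 − 0.590 = 0.41
- p = 0.8: 1 − 0.328 = 0.67
- p = 0.5: 1 − 0.031 = 0.97

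Let k participants have little deficit and gain a fraction f of the change d seen in the others. The mean change falls by d × k(1 − f)/5. For f between 0 and 0.5, that is 0.10d to 0.20d with k = 1, and 0.20d to 0.40d with k = 2.

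In units of the SD of change, the 95% confidence half-width at n = 5 is 2.776/√5 = 1.24. Across k = 1 or 2:

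| Assumed d (SD) | Loss in mean change (SD) |
|---|---|
| 0.5 | 0.05 to 0.20 |
| 1.0 | 0.10 to 0.40 |

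In these cases the loss is well below the half-width, but it grows in proportion to d, so it would not be negligible for a very large effect. The mean that includes such participants is still the right mean for the enrolled population; it is a biased figure only if labelled as the effect in PIGD.

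**The case for a change.** The strongest case for a change is that PIGD is a stated indication, not a stray phrase, since a background heading repeats it. A cardinal symptom of the disease need not be present in each participant, and assessments on medication with DBS active measure only the deficit that remains under both treatments. With five people one participant matters, and a pooled ANOVA does not show who had room to improve. Aligning one phrase and adding one descriptive table would cost almost nothing.

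The facts in this stand: no criterion requires a deficit, and the stated analysis is for the whole group. A result from this trial therefore should not be reported as specific to PIGD.

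The need for a change does not follow. The rewording would bring the goal into line with what the Approach already says, and it alters no estimate, test or decision. The table is a reporting choice an analyst of a five-person study can make from data already scheduled; it leaves eligibility and analysis as they are. Nor is it accurate to call the enrolled group PD with DBS in general, since four exclusions narrow it.

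**Conclusion.** The mismatch is real in the wording and has no consequence for the analysis. Followed as written, the plan supports a conclusion about people with PD and DBS who meet the eligibility criteria, which is the efficacy population named in the Approach. The safety and tolerability hypothesis does not depend on PIGD status, and broad entry suits it. Because MMT also targets cognition and dual-task impairment, people with little gait deficit may still benefit, so excluding them is not clearly a gain.

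The size cannot be fixed from the documents. The probabilities of 0.41 to 0.97 and the loss of 10% to 40% of the mean change rest on assumed PIGD shares and assumed gain fractions. They show that mixed entry is plausible and that a pooled mean could be diluted as a measure of effect in PIGD. They do not show an error in a plan that claims no power and no PIGD-specific estimate. This is a point for the reader to bear in mind when interpreting the results, and no change to the plan is called for.

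### The preliminary-efficacy aim has no lead outcome, task condition or time contrast, so any of about 6 to 11 function tests could be reported as the efficacy result

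*Combined protocol and SAP*

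**What the plan says.** - **Table 1 (Outcome Metrics).** Nine assessments are listed, each with an entry in a column headed "Primary Outcome". No row is marked secondary or exploratory, and no study-level primary endpoint is named elsewhere.
- **Rows with more than one possible score.** The walk test is described as "Distance traveled during a 2-minute period under single- and dual-task conditions". The Timed Up and Go and the cognitive measure are likewise taken under both task conditions. Postural sway is described as "Amount of sway in multiple directions", with one metric, a sway distance.
- **APPROACH.** The study is to assess safety and preliminary efficacy, but the one hypothesis is "It is hypothesized that the DART platform will result in few adverse events and will be well-tolerated by individuals with PD and DBS". No efficacy hypothesis is given.
- **Power and Statistical Analysis.** Apart from the remark on sample size, the whole plan is "A repeated measured ANOVA will be used to compare the group at the three different time points (baseline, midpoint, and end of treatment"). It names no outcome, alpha, lead contrast among the three visits or multiplicity rule, and it does not say that results are descriptive.

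**The concern.** Safety has a matching outcome: the hypothesis expects few adverse events, and the first row of Table 1 counts them. Efficacy has no such link. An analyst who follows the plan exactly could test every function score at all three visits and present whichever one moved as the preliminary efficacy finding, without departing from anything written.

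If one of several equal-rank scores reaches nominal significance in five people, readers cannot tell whether it was the result the study set out to look for. That matters because a preliminary result of this kind is likely to guide the choice of endpoint for a later trial.

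**Working it through.** The documents give no alpha, error rate or power figure, so there is no stated number to reproduce. The check counts the available function tests and then finds how often at least one would be significant by chance.

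**Step 1: count the tests.** Adverse events (safety) and usability (a rating of the technology) are left out.

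| Way of counting | Sum | Tests |
|---|---|---|
| One test per function row: walk, MDS-UPDRS III, TUG, sway, cognition, ABC | 1+1+1+1+1+1 | 6 |
| The same, with falls counted as a function outcome | 6+1 | 7 |
| Single- and dual-task scores tested separately; one sway metric; no falls | 2+1+2+1+2+1 | 9 |
| The same, plus either falls or a second sway direction | 9+1 | 10 |
| The same, plus both | 9+2 | 11 |

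Further sway directions, or pairwise comparisons between visits, would raise the count.

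**Step 2: independent outcomes.** Assume 0.05 per test and no true change. The chance of at least one nominally significant result among k tests is 1 − 0.95^k:

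- k = 6: 1 − 0.7351 = 26%
- k = 7: 1 − 0.6983 = 30%
- k = 9: 1 − 0.6302 = 37%
- k = 10: 1 − 0.5987 = 40%
- k = 11: 1 − 0.5688 = 43%

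**Step 3: correlated outcomes.** These scores come from the same people at the same visits, so independence is an upper case. Null trials were simulated with 5 participants, 3 visits, normal errors and the same correlation between every pair of outcomes. Each outcome was tested by the repeated-measures F test on 2 and 2 × (5 − 1) = 8 degrees of freedom, with at least 20,000 runs per cell. Results are good to about one percentage point.

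| Tests | Correlation 0.3 | 0.5 | 0.7 | 0.9 |
|---|---|---|---|---|
| 6 | 25% | 22% | 19% | 12% |
| 7 | 29% | 25% | 20% | 13% |
| 9 | 35% | 29% | 23% | 14% |
| 10 | 37% | 32% | 25% | 15% |
| 11 | 39% | 33% | 26% | 15% |

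**Step 4: effect of naming one test.** With one pre-named outcome and contrast, the chance of a false-positive lead result is the assumed 5%. Keeping ten equal-rank tests under Bonferroni would instead need 0.05/10 = 0.005 per test.

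**The case against.** The strongest reply is that the heading is being read too literally. The table is titled as a list of metrics, and the column holds units, counts and total scores, so the natural reading is the main measurement from each assessment. That stands: a reader might infer nine co-primary endpoints, and the documents do not support it. The natural reading does not close the gap, though, because it leaves no efficacy outcome designated at all.

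A reader might also infer that every Table 1 outcome goes through the ANOVA. The text does not say so. The ANOVA is the only method given, and motor and non-motor assessments are scheduled at the three visits it compares, so applying it to the function scores is a reasonable inference. It fits poorly for intervention-related adverse events and for usability of the device, neither of which has a natural pre-treatment value.

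Nor is ten a minimum. Table 1 gives a single sway metric and does not say that each direction, or each task condition, will be tested separately.

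Finally, this is a single-group study of up to five people that calls itself preliminary. It states efficacy as an aim and makes no claim of it, and no decision rule hangs on a p-value. Even a pre-named test would be weak evidence here. This limits how much the fix can gain. It would answer the concern fully only if the plan were descriptive, and the plan specifies an inferential test.

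**Conclusion.** The concern holds in a limited form. The safety aim has a hypothesis and an outcome that match. The preliminary-efficacy aim has no lead outcome, task condition or contrast, and the remaining scores are not labelled exploratory.

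The chance of at least one nominally significant function result when nothing has changed runs from 26% (6 tests) to 43% (11 tests) under independence, and from about 12% to 15% at a correlation of 0.9. Even the lowest of these is more than twice 5%. The range rests on three assumptions that the documents neither state nor contradict: a 0.05 threshold, use of the ANOVA for each function score, and the correlation between outcomes.

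The point should be addressed. It affects what can be said about efficacy, and it does not affect the safety assessment or the feasibility of the study.

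**What to change.** 1. Rename the Table 1 column 'Metric'.
2. Declare the number of intervention-related adverse events the primary outcome, to match the hypothesis. Include tolerability only if a metric is defined for it, since Table 1 has none.
3. Pre-name one efficacy outcome with its task condition and time contrast. One example is dual-task Two Minute Walk distance, end of treatment versus enrollment. State that this is the planned contrast within the repeated-measures ANOVA, so that it and the three-visit comparison are not rival results.
4. Label all other scores exploratory, including each additional task condition and sway direction. Report estimates with confidence intervals for all of them, and base no efficacy statement on an unadjusted p-value from them.

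The cost is one column heading and a few sentences, plus a definition if tolerability is kept. Visits, measurements and participant numbers do not change. The small downside is that a change seen only in another outcome can be called exploratory and nothing more.

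### Table 1 counts only intervention-related adverse events: falls of any cause reach the Fall Diary, but a non-fall event judged unrelated enters no listed outcome

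*Combined protocol and SAP*

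**What the plan says.** In Table 1 (Outcome Metrics) the adverse-event row is limited by cause in both columns. The description reads "Such as falls, dizziness, and others as a result of the intervention" and the metric reads "Number of serious and non-serious adverse events related to the intervention".

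The only other row that counts events is the Fall Diary, whose metric is "Number of falls" with no condition on cause.

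The Power and Statistical Analysis section adds no further count. Its one analysis sentence says "A repeated measured ANOVA will be used to compare the group at the three different time points".

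Safety comes first in both the Project Goal and the Approach section. The hypothesis there is that DART will produce few adverse events and be well tolerated. No number is attached to few. There is one arm, with up to five participants.

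**The concern.** With no comparator, the safety result is a bare count, and whether an event enters that count depends on a judgement of cause. Everyone receives DART, so that judgement is made knowing the participant was treated. Participants have Parkinson's disease and an implanted stimulator, and they are seen about an hour after medication, so an event such as dizziness may have several plausible causes.

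Some events during the study fall outside the row by definition. Data Collection schedules assessments "at the following time points: enrollment, midpoint, and end of treatment", and these include the Timed Up and Go: "Stand from chair, walk 3 meters, turn, return to chair under single- and dual-task conditions". Dizziness during that test at enrollment, which the analysis section treats as baseline, would come before treatment and could not result from DART. It would appear in no row.

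At stake is whether a reader of the listed outcomes can see how far a low count rests on attribution.

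**Working it through.** The plan gives no figure to reproduce. The sample size is justified only by the preliminary nature of the study, and no event rate is stated. The check is a reading of the table followed by simple counting.

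**Step 1: rows.** Table 1 has nine rows. Two count events (adverse events, Fall Diary). The other seven are performance or questionnaire measures: Two Minute Walk Test, MDS-UPDRS III, Timed Up and Go, postural sway, cognitive performance, usability surveys and ABC. 9 - 2 = 7.

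**Step 2: where a single event is counted.** This assumes that every fall reaches the diary and that both rows cover the same period.

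| Event | Adverse-event row | Fall Diary | All-cause count |
|---|---|---|---|
| None | 0 | 0 | 0 |
| Non-fall, related | 1 | 0 | 1 |
| Non-fall, unrelated | 0 | 0 | 1 |
| Fall, related | 1 | 1 | 1 |
| Fall, unrelated | 0 | 1 | 1 |

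Only the unrelated non-fall matches the no-event line on both listed rows.

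**Step 3: what the two listed totals determine.** Let R be the related count, F the diary total, f the number of related falls and U the number of unrelated non-falls. The all-cause total is

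A = R + (F - f) + U.

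Since f lies between 0 and the smaller of R and F, the listed totals give A at least as large as the larger of R and F. They give no upper limit, because U appears nowhere. The diary does cap f: F = 0 means no related falls, and F = 1 means at most one.

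**Step 4: an example.** Take R = 2 and F = 2.

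- f = 0: A = 2 + 2 + U = 4 + U
- f = 1: A = 2 + 1 + U = 3 + U
- f = 2: A = 2 + 0 + U = 2 + U

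The number of falls is known (2) in all three cases. The related split of the falls is uncertain only if bare totals are reported. U is unknown throughout.

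**Step 5: what the added count gives.** A - R = (F - f) + U is exactly the number of events judged unrelated. If A = R, the low count does not depend on any event having been judged unrelated.

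**The case against.** The strongest reply is that nothing here is an error. The hypothesis concerns what DART will bring about, and a related count measures that directly. The last column of Table 1 is headed as the primary outcome for each assessment, so it may give a lead metric and need not exhaust what is recorded or reported. The added count mixes in background disease. With no comparator it shows how many events were judged unrelated, not whether those judgements were right.

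Most of this stands. The metric does not contradict the hypothesis, and the point is about a missing companion count. What remains is that no listed outcome or analysis supplies that count, although safety is the first aim.

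A reader might infer more than the documents support:

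- **That unrelated events go unrecorded.** The text does not say so. It shows only that no listed outcome counts them.
- **That attribution leans towards unrelated.** Nothing supports a direction. The supplied text names no role or criteria for judging relatedness, but some pages were removed and Figure 1 is not shown, so this is not counted as a defect.
- **That the Fall Diary is no check even for falls.** It is an all-cause total for falls and an upper limit on related falls. It is a partial check.
- **That the safety conclusion would change.** With no threshold for few and no stated decision rule, no changed decision can be shown.

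**Conclusion.** The point holds in a narrow form. One class of event, the non-fall judged unrelated, is outside every listed outcome, whether serious or not. Each such event moves the listed counts by 0 and an all-cause count by 1. That illustrates the counting rule and does not estimate bias, since no event rate or share of related events is assumed.

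The conclusion rests on reading Table 1 and the analysis section as the full set of listed outcomes. If the sponsor already intends to report events of any cause, the remedy is only to say so. Rating: minor, a cheap improvement.

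**What to change.** Keep the related count. Add to the adverse-event row of Table 1 a count of adverse events of any cause, serious and non-serious, from enrollment to end of treatment, split into falls and non-falls. Report it beside the related count. If the diary covers the same period, the fall part should agree with the diary total, so the new information is mainly the non-fall part.

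The cost is one added metric in at most five people over a treatment period of no more than ten weeks. If such events are already recorded, the cost is in reporting only. The all-cause number will be higher. It will include background disease events and any that occur before the first DART session, and it cannot by itself separate harm from DART from that background; the text should say so. With so few participants, event detail could identify someone, so only aggregate counts should be published.

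### With no missed-visit rule, the planned repeated-measures ANOVA would in standard use drop a participant for one missed midpoint; a mixed model keeps that person's other visits, for a modest gain

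*Combined protocol and SAP*

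**What the plan says.** The analysis plan is two sentences in the Power and Statistical Analysis section. The first justifies the size: "The sample size (N=5) is reflective of the preliminary nature of the study". The second names the method: "A repeated measured ANOVA will be used to compare the group at the three different time points", meaning baseline, midpoint and end of treatment.

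Five is a ceiling. Under DART Platform and Intervention: "Up to five individuals with PD and DBS will receive the DART intervention". The Data Collection paragraph states: "Assessments of motor and non-motor function will be completed for all participants at the following time points: enrollment, midpoint, and end of treatment". That expresses an intention to collect every visit. It does not say what happens to a participant who misses one.

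The Approach paragraph gives the study's purpose as "to determine the safety and preliminary efficacy of the DART platform on individuals with PD and DBS". The ANOVA is the only analysis named for the efficacy part. The document contains no missing-data rule, analysis set, imputation, covariance structure, sphericity correction or dropout assumption.

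**The concern.** A one-group repeated-measures ANOVA, as usually run, needs all three values from each participant for each outcome. Someone who misses the midpoint, or a single test at the midpoint, then drops out of that outcome's analysis altogether. The enrollment and end values, which carry the main contrast, have been collected and are thrown away.

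With at most five people that is a visible loss of precision. Table 1 lists several tests, some under both single- and dual-task conditions, so gaps can differ between outcomes and the results could describe different sets of people. If the handling is not fixed in advance, it may be chosen after the results are seen. Dropping incomplete participants also requires, in general, that missing values be unrelated to the participant's course.

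**Working it through.** **Inputs from the document.** N is at most 5, there are 3 visits, and the ANOVA has one group. The sample size has no alpha, power, effect size or SD behind it, so there is no figure of the plan's own to reproduce.

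**Inputs assumed.** Miss rates are 5% and 10% for each post-enrollment visit, independent across visits and people. The intraclass correlation (ICC) is 0.5 to 0.9. The document gives none of these.

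**1. People lost.** One person is 1/5 = 20% of the sample if five enrol, 1/4 = 25% if four, and 1/3 = 33% if three. With five enrolled and one missed midpoint, 14 observations exist and the ANOVA on four people uses 12. A standard repeated-measures ANOVA routine, given such data, refused them as unbalanced.

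**2. Chance of the relevant pattern.** One person misses the midpoint but attends the end with probability p(1 - p). For at least one of five:
- p = 0.05: 1 - (1 - 0.05 × 0.95)^5 = 1 - 0.9525^5 = 0.216
- p = 0.10: 1 - (1 - 0.10 × 0.90)^5 = 1 - 0.91^5 = 0.376

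**3. Precision with one missed midpoint.** The unit is the within-person residual SD.
- ANOVA on four people: variance of the end-minus-enrollment change 2/4 = 0.50; error df 2 × (4 - 1) = 6; half-width 2.447 × √0.50 = 1.73.
- All 14 observations: all five people have both end values, so the variance is 2/5 = 0.40, the same as with no gap; error df 14 - 5 - 2 = 7; half-width 2.365 × √0.40 = 1.50.
- No missing visit: error df 8, half-width 1.46.

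The ratio 1.496/1.730 makes the interval 13.6% narrower. Allowing for the residual SD being estimated (expected values 0.959 and 0.965 of the true SD at 6 and 7 df), the half-widths are 1.66 and 1.44, which is 13.1% narrower. A simulation of 4,000 runs gave 12.9%.

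**4. Other patterns.** The variance is c′(Σ Xᵢ′Vᵢ⁻¹Xᵢ)⁻¹c, with Vᵢ = I + [ICC/(1 - ICC)]J and c the end-minus-enrollment contrast. The comparator is always the ANOVA on four people.

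| One person misses | Variance, ICC 0.5 to 0.9 | df | Interval narrower by |
|---|---|---|---|
| midpoint only | 0.400 | 7 | about 13% |
| end only | 0.467 to 0.474 | 7 | about 5-7% |
| both | 0.475 to 0.495 | 6 | 2.5% down to 0.5% |

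The last two rows treat the variance ratio as known, so they are slightly favourable to the mixed model.

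**5. Illustrative power.** Assume alpha 0.05 and a linear change of 2 residual SDs. Power is 64% with complete data, 49% after dropping the person who missed the midpoint, and 61% with the mixed model. For changes of 1 and 3 SDs the figures are 20/15/19% and 94/83/93%.

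**6. Agreement on complete data.** In 200 simulated data sets of five people by three visits, the random-intercept REML F equalled the ANOVA F in all 157 with a positive between-person variance estimate. It differed in 41 of the 43 where the estimate was zero. At N = 5 the probability that the ANOVA estimate of that variance is negative, so that REML returns zero, is 9.8%, 3.1% and 0.3% at assumed ICCs of 0.5, 0.7 and 0.9.

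**The case against.** The plan never says that incomplete participants are excluded. It names a family of methods in one sentence, and an ANOVA with participant and visit as factors can be fitted to all 14 observations; that is where the 7 df come from. This objection stands: exclusion is the usual consequence of the named method and not a stated rule. It does not remove the need to say which will be done.

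No document supports a miss rate of 5% or 10%, and Data Collection intends every visit to take place. If every visit does, nothing is lost. This also stands, so the probabilities are conditional.

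A reader might pair the 13% with the chance that anyone misses either post-enrollment visit, which is 1 - 0.95^10 = 40% or 1 - 0.90^10 = 65%. Those figures include missed end visits, where the gain is about half as large or less. For the 13% case the probabilities are 22% and 38%.

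The mixed model has assumptions of its own. It needs values to be missing at random, which five people cannot test, and a random intercept keeps compound symmetry. Different people could still contribute to different outcomes.

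The only stated hypothesis concerns few adverse events and good tolerability, and this change does not touch it.

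**Conclusion.** The point holds as a modest, inexpensive improvement to the efficacy analysis. The plan names a method that in standard use drops a participant with any gap, in a study of at most five, and gives no rule for gaps. When one person misses only the midpoint, using all visits narrows the enrollment-to-end interval by about 13% and restores nearly all the precision of complete data. For a person who truly drops out it recovers little.

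These sizes rest on compound symmetry, on missing at random and, for the probabilities, on assumed and independent miss rates.

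Two stronger readings are not supported. One is that the mixed model always gives the ANOVA's answer on complete data; it does so only when the between-person variance estimate is positive. The other is that the safety conclusions are at risk; adverse-event counts do not pass through this analysis.

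**What to change.** Replace the ANOVA sentence in Power and Statistical Analysis with wording such as:

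*Each continuous outcome measured at all three visits will be analysed with a linear mixed model with visit (three levels) as fixed effect and participant as random intercept, fitted by REML with Kenward-Roger degrees of freedom, using all available visits of all enrolled participants. The number of participants and visits behind each estimate will be reported.*

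List the outcomes covered. Adverse events and falls are counts, and the usability scale has no natural enrollment value, so they need their own description.

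The small-sample degrees of freedom are essential: a chi-square test in place of F(2,8) has a true type I error of about 10.7% at a nominal 5%. An unstructured covariance should not be substituted, since it is barely estimable with five people. With so few participants, estimates with intervals and individual trajectories should carry more weight than the p-value.

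The cost is this wording, with no added data, visits or staff. The result may differ slightly from the ANOVA when the variance estimate is zero.
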